		Data on all blood and urine tests will be measured separately: FBC, serum transaminases, serum creatinine, thyroid function and urinalysis between the index date and 30 days prior to and	
	During Infusion	including the index date, for each course.	
	HR and BP	During infusion	
	Platelets on days three and five of the first course (day three only for any subsequent course)	HR and RP measured separately on each day of	
		course (index onwards). Platelets measured on	

December 2023 Version number: 3.1

	day 3 and day 5 of the first course and day 3 of any subsequent course.
Post-Infusion Monthly: FBC, serum creatinine, serum transaminases, and urinalysis with microscopy Every three months: Thyroid function tests.	Post-Infusion Evidence of monthly monitoring defined as: Evidence that each test is carried out within the designated testing period e.g., index date $+30$ days ± 15 days.
	Evidence of monitoring every three months defined as: Evidence that a thyroid function test is carried out within the designated testing period e.g., index date +90 days \pm 30 days

AI=autoimmune; ATC=Anatomical Therapeutic Chemical; BP=blood pressure; DMT=disease modifying therapy, ECG=electrocardiogram; FBC= full blood count; HR=heart rate; HIV=human immunodeficiency virus; ICD=International Classification of Diseases; IV=intravenous; MS=multiple sclerosis; SAP=Statistical Analysis Plan; UK=United Kingdom

December 2023 Version number: 3.1

Table 3: Feasibility of each data source in meeting objectives 1a (indication) and 1b (contraindication). Grey sections
indicate not measurable

	Type of data	Indication	Contraindication	Notes	
Czech Republic	MS patient registry and patient chart data	Yes Data on previous treatments	Hypersensitivity to alemtuzumab or excipients	Contraindications and MRI data recorded in patient charts; manual	
		MRI and relapse history directly available in MS registry data	HIV	extraction required	
			Severe active infections until complete resolution		
			Uncontrolled hypertension		
			History of arterial dissection of the cervicocephalic arteries		
			History of stroke		
			History of angina pectoris or myocardial infarction		
			Known coagulopathy, on anti- platelet or anti-coagulant therapy		
			Other concomitant AI diseases (apart from MS)		

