9.5.3 Secondary use of data from an ongoing cohort study: Germany TREAT-MS

The TREAT-MS study is a non-interventional long-term, multi-centre, cohort study that documents patients with RRMS treated with LEMTRADA.(15) The protocol aimed to recruit 1600 patients from across 400 MS centres in all parts of Germany (Appendix 3). The sites included different types of centres including neurologists and physicians in neurology departments or outpatient clinics as well as private neurologists in specialized MS centres. As such, the study population includes a broad "typical" alemtuzumab patient population as treated under real-life conditions in Germany.(16) The latest published interim analysis informs that as of February 2020, 883 patients were included in the cohort, recruited by 118 physicians.(16) The recruitment period was from 2013 to 2020, with last patient first visit in December 2020, after which the total study population consisted of over 900 patients. Included patients continue to receive indicated courses after this time and follow-up continues for up to 60 months for each patient.

The primary goal of the TREAT-MS study is to determine and assess the implementation of the LEMTRADA Risk Management Plan (RMP) in routine clinical practice. Therefore, the study database contains information for MS disease characteristics that inform on the indication, contraindications as well as monitoring pre, during and post-infusion. The objectives of the TREAT-MS study thus overlap with the objectives of the current DUS. Thus, the data collected in the TREAT-MS study can be used as a secondary source of data to satisfy the completion of the DUS. (17)

Details on data collection and storage can be found in the TREAT-MS protocol (Appendix 3). Briefly, data are entered to the electronic case report form (eCRF) with the guidance of the Multiple Sclerosis Documentation System (MSDS 3D) LEMTRADA TREAT-MS module.(18) Baseline data are collected up to six weeks prior to LEMTRADA administration, which include current and retrospective data on the patient and MS. Thereafter, follow-up data are collected as per routine care for up to a maximum of 60 months after first administration of LEMTRADA.

The structured CRF collects data on medical history, type of MS, number of relapses in the 2 years prior to enrollment, prior treatments for MS, contraindications, and examinations prior to,

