9.8.2 Secondary analysis

Objective 2a: Cohort entry and follow-up:

The index date will be defined as the date of LEMTRADA course initiation, which must occur after implementation of the newly revised SmPC. Each course will be identified as a new use course or a continuing course, see Section 9.3 for definitions of new and continuing use. On the index date, the following proportions will be calculated:

- Cardiac monitoring prior to infusion
 - Numerator=number of courses that had ECG, BP, and HR monitoring (separately) between the index date and 30-day period prior to index date³. The test dates closest to course start date will be taken.
 - Denominator=number of courses in the study period.
- Blood and urinalysis monitoring prior to infusion.
 - Numerator=number of courses that had evidence for FBC, serum transaminases, serum creatinine, urinalysis with microscopy and test of thyroid function (all separately) between the index date and 30-day period prior to index date⁴.
 - Denominator=number of courses in study period. Proportions will be stratified on new and continuing use as well as course number. See Table 7 for example table shells.

A period of 30 days was selected to construct the testing period prior to infusion based on knowledge of clinical practice and the time usually taken for tests to be administered and results received in order to prepare for infusion.

³ In TREAT-MS, the monitoring of BP and HR prior to course is checked at index date only; there is no look-back period.

⁴ In TREAT-MS, for the new courses, blood and urinalysis monitoring prior to infusion is collected at screening and/or at index date. The screening visit occurs at least 6 weeks prior to the first infusion. For continuing courses, this is collected throughout the follow-up and thus, the 30-day period will apply.

Between the index date and index date + 5 days for new courses or + 3 days for continuing courses (index date included), the following proportions will be calculated:

- Cardiac monitoring (HR and BP) during infusion.
 - Numerator=number of courses with evidence for HR and BP on each day for the first course (or first three days for subsequent courses).
 - Denominator=number of courses in study period.
- Platelets on day three and day five of infusion if the first course, otherwise day three for subsequent courses.

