*Pre-existing diseases and adverse events are coded with Medical Dictionary for Regulatory Activities (MedDRA) Lowest Level Term (LLT) codes. The dates of all variables are available through the visit date.

17 APPENDIX 5

ENCePP Checklist for Study Protocols (Revision 4)

Adopted by the ENCePP Steering Group on 15/10/2018

The European Network of Centres for Pharmacoepidemiology and Pharmacovigilance (ENCePP) welcomes innovative designs and new methods of research. This Checklist has been developed by ENCePP to stimulate consideration of important principles when designing and writing a pharmacoepidemiological or pharmacovigilance study protocol. The Checklist is intended to promote the quality of such studies, not their uniformity. The user is also referred to the ENCePP Guide on Methodological Standards in Pharmacoepidemiology

(https://www.encepp.eu/standards_and_guidances/checkListProtocols.shtml), which reviews and gives direct electronic access to guidance for research in pharmacoepidemiology and pharmacovigilance.

For each question of the Checklist, the investigator should indicate whether or not it has been addressed in the study protocol. If the answer is "Yes", the section number of the protocol where this issue has been discussed should be specified. It is possible that some questions do not apply to a particular study (for example, in the case of an innovative study design). In this case, the answer 'N/A' (Not Applicable) can be checked and the "Comments" field included for each section should be used to explain why. The "Comments" field can also be used to elaborate on a "No" answer.

This Checklist should be included as an Annex by marketing authorisation holders when submitting the protocol of a non-interventional post-authorisation safety study (PASS) to a regulatory authority (see the Guidance on the format and content of the protocol of non-interventional post-authorisation safety studies). The Checklist is a supporting document and does not replace the format of the protocol for PASS presented in the Guidance and Module VIII of the Good pharmacovigilance practices (GVP).

Study title:

A NON-INTERVENTIONAL POST-AUTHORISATION SAFETY STUDY TO INVESTIGATE DRUG UTILISATION AND SAFETY MONITORING PATTERNS FOR LEMTRADA (ALEMTUZUMAB)

EU PAS Register[®] number: EUPAS42540 **Study reference number (if applicable):** DUT0008 and VV-PV-0404767

Secti	on 1: Milestones	Yes	No	N/A	Section Number

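### Footnote 4 appears to lift the 30-day pre-infusion window for German new courses, so blood tests recorded only at an early screening visit can be credited as adherent

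*Protocol*

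**What the plan says.** Section 9.8.2 counts a course towards pre-infusion blood and urine monitoring if each test is evidenced "all separately) between the index date and 30-day period prior to index date". Table 2 in Section 9.3 gives the same span for every course; its list of tests ends with thyroid "function and urinalysis between the index date and 30 days prior to and" including the index date. The choice is justified: "A period of 30 days was selected to construct the testing period prior to infusion based on knowledge of clinical practice", together with the time needed to run the tests and receive results.

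Footnote 4 to that numerator deals with TREAT-MS. For new courses, "blood and urinalysis monitoring prior to infusion is collected at screening and/or at index date", and "The screening visit occurs at least 6 weeks prior to the first infusion". Then: "For continuing courses, this is collected throughout the follow-up and thus, the 30-day period will apply".

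Two other places describe the same early visit. Section 9.5.3 says: "Baseline data are collected up to six weeks prior to LEMTRADA administration". The TREAT-MS observation plan (Appendix 3, Section 6, note under the schedule) asks for at least 6 weeks only where immunisations are still outstanding.

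Appendix 4 lists the TREAT-MS variables used in this study. For objective 2a before infusion it gives both baseline and the first infusion date as sources for blood count, transaminases, thyroid function and creatinine, but only the first infusion date for urine status. Its closing note says: "The dates of all variables are available through the visit date".

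**The concern.** The general rule and the German new-course rule do not measure the same thing. If a screening test counts whatever its age, a German patient starting treatment can be recorded as tested before infusion on a result that would be scored as missed in a Czech or UK patient, or in the same German patient at the next course.

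Two planned displays depend on the rule being common. Section 9.8.2 stratifies pre-infusion monitoring by new and continuing use and by course number; in Germany those strata would use different windows. Table 7 sets Germany beside the other countries, with a possible pooled row and no mark for a different definition. A difference seen in either could come from the rule and not from practice. The study exists to measure compliance with risk minimisation, so crediting tests outside its own window matters even when the numbers are small.

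**Working it through.** No stated figure needs reproducing; the check sets the windows side by side and then bounds the effect.

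**Timing**
- General window (9.8.2, Table 2): day 0 to day 30 before the index date.
- Footnote 4: at least 6 weeks = 6 × 7 = 42 days or more. 42 − 30 = 12, so on this wording a screening test lies at least 12 days outside the window.
- Section 9.5.3: up to 6 weeks = 0 to 42 days. A test at 0 to 30 days qualifies; one at 31 to 42 days does not.
- Observation plan: 42 days or more only for patients awaiting immunisation; no such minimum for the rest.
- Index-date tests qualify on every wording.

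The three statements cannot all describe the same visit. Under each of them, some screening tests may be older than 30 days.

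**Tests affected**
Full blood count, transaminases, creatinine and thyroid function have a baseline source in Appendix 4. Urinalysis does not, so it is unaffected.

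**Size**
Table 5 (2023 interim) gives 8 German new users and 72 German patients in cohort 2a. The row totals agree: 27 + 63 + 16 + 8 = 114 and 87 + 107 + 69 + 72 = 335.

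Let k be the number of German new courses whose only test was at a screening visit more than 30 days before the index date. The documents do not give k, so the full range 0 to 8 is shown. Assuming all 8 courses are credited under footnote 4, the figure under the 30-day window is (8 − k)/8, with exact 95% intervals. The all-course shift is k/72, assuming one course per patient.

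| k | German new courses, 30-day rule | Shift, all German courses |
|---|---|---|
| 0 | 8/8 = 100% (63.1 to 100) | 0 |
| 2 | 6/8 = 75% (34.9 to 96.8) | 2.8 points |
| 4 | 4/8 = 50% (15.7 to 84.3) | 5.6 points |
| 8 | 0/8 = 0% (0 to 36.9) | 11.1 points |

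Each such course moves the German new-course figure by 1/8 = 12.5 points. More than one course per patient would enlarge the denominator and shrink the all-course shift. In a simple sum over all sources' new users, the ceiling is 8/114 = 7.0 points.

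**Whether the plan catches it elsewhere**
The only objective 2a sensitivity analysis in Section 9.8.4 concerns heart rate and blood pressure on the index date. Section 9.11 does not mention the window difference.

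**The case against.** **The scoring rule is not explicit.** Footnote 4 says where the data are collected; it does not say that a screening test older than 30 days counts. The numerator it annotates keeps the 30-day window, and the amendment table in Section 5 presents the footnote as clarifying which data are available. This stands as a limit on certainty. But stating that the 30-day period will apply to continuing courses makes little sense unless it does not apply to new ones, and Appendix 4 names baseline as an objective 2a source. If the sponsor means otherwise, two programmers could still score the same course differently.

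**The timing is unsettled.** A reader might infer that every German screening test fails the window. That rests on one sentence that Section 9.5.3 contradicts and the observation plan makes conditional, so the documents do not support it.

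**Net bias is not established.** On the same records, a 30-day filter can only lower or leave the German figures. But for new courses TREAT-MS records these tests only at screening and/or the index date, so a test done in between may be missing. A strict filter could then understate adherence against sources with a full 30-day look-back. The observation plan also accepts last available values, and dates come only through the visit date, so visit and test dates may differ. These points stand and shape the fix.

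**Reach is small and the exception is disclosed.** There were 8 new users at the 2023 interim, TREAT-MS recruitment closed in December 2020, stratified analyses in Section 9.8.4 depend on cell size, and pooling is conditional. This limits the consequence, but a footnote does not make the figures comparable.

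**Conclusion.** The point holds in this form: followed as written, footnote 4 can credit German new courses with blood tests taken 42 or more days before infusion, while German continuing courses and the general definition use 30 days. The three statements of screening timing also conflict. That the 30-day limit is lifted is a strong inference, not an explicit statement.

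The effect is 12.5 points on the German new-course figure for each screening-only course, with a ceiling of about 11 points on the German all-course figure. This rests on the 2023 interim counts and one course per patient. A reader might infer an overstatement of 100 points for German new users. That is only the extreme in which all 8 were tested solely at an early screening visit; the documents give no such count, and index-date tests always qualify. Urinalysis falls outside the point. The objective is secondary and the numbers are small, but the correction is worth making before the final report.

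**What to change.** - Reconcile the screening timing in footnote 4, Section 9.5.3 and the observation plan note.
- State in footnote 4 that blood count, transaminases, creatinine and thyroid tests for TREAT-MS new courses are scored against the 30-day window, using the recorded visit date.
- Report courses whose only test was at a screening visit more than 30 days before the index date as a separate category, and give the German new-course percentages with and without counting them as adherent.
- Mark the German row in Table 7 to show how its new courses were measured.

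The cost is an edited footnote, a table note, and a date filter with one extra category in the German programme. The German new-course percentages may fall and could understate adherence, because tests between screening and the index date may not be captured and the visit date may differ from the test date. The report should say so beside the figures.

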Multiple sclerosis (MS) registry data from Czech Republic, administrative data from Belgium, hospital chart data from the UK, and secondary data use from a cohort study in Germany. The Belgian data source contributed data for analyses up to the interim report of 2022. Results of these analyses will be included in the interim report of 2023 and the final report of 2024, but no new analysis will be carried out.

Study size:

This is a descriptive study. There are no formal hypothesis tests and thus traditional sample size calculations to estimate power are not appropriate. Instead, the focus is on obtaining a sample that is representative of the main usage countries, to achieve geographical diversity where practicable and to allow some precision in calculation of descriptive proportions. A feasibility analysis was carried out in 2022 to investigate numbers of eligible patients and ability to measure variables as required for the successful conduct of the study across all data sources.

Data analysis:

In each individual data source, descriptive proportions will be calculated as follows:

- Prescribed in accordance with the newly revised indication (objective 1a): numerator = number of patients with revised indication, denominator=all patients initiating their first course of LEMTRADA after implementation of the revised EU SmPC January 2020.
- New or continuing user with no contraindications at time of course initiation post EU SmPC change (objective 1b): numerator=number of courses without contraindications, denominator=all LEMTRADA courses post EU SmPC change.
- Receive advised cardiac monitoring (electrocardiogram (ECG), heart rate (HR), blood pressure (BP)) and blood testing prior to, along with HR/BP and platelet testing during LEMTRADA course (objective 2a): numerator=number of courses with each unique test prior to and during infusion, denominator=all LEMTRADA courses post EU SmPC change.
- Percentage adherence to each test will be calculated, at the patient level, to monthly monitoring for up to 48 months since last infusion for FBCs, serum creatinine, serum transaminases and urinalysis with microscopy, and monitoring every three months for

thyroid function (objective 2b): numerator=number of specific tests received, denominator=number of testing periods required.

Milestones

- Report on feasibility analysis **Q3 2021**
- Annual interim progress report **Q4 2021**
- Full feasibility report **Q2 2022**
- Annual interim progress report Q4 2022

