- Percentage adherence to monthly FBC, serum transaminases, serum creatinine, and urinalysis with microscopy monitoring e.g., the number of each specific test carried out within designated testing periods (e.g., index +30 days ±15 days) divided by the total number of testing periods for each patient. Adherence to safety monitoring will be calculated for each test and for each patient and then the average for each test across all patients will be presented in each data source (see Table 9for example table shells).
- Percentage adherence to thyroid monitoring every three months e.g., the number of tests carried out within designated testing periods (e.g., index +90 days ±30 days) divided by the total number of tri-monthly testing periods for each patient. Adherence to thyroid monitoring will be calculated for each patient and then the average across all patients will be presented in each data source (see Table 9for example table shells).

To verify that the designated testing periods (± 15 days for monthly tests and ± 30 days for tests every three months) are appropriate, the distribution of days around the intended testing day was tested in the feasibility analysis.

To capture monitoring post-infusion, follow-up must be sufficient for monitoring to occur. The follow-up time for each course will be described and patients excluded from the analysis at the point that follow-up ends. Patients will be followed until 48 months after the last infusion, receipt of another LEMTRADA course, the end of study (Q1 2024), end of data in each data source or death/emigration as recorded in each data source, whichever occurs earliest.

Follow-up time will reset at the point of an additional course. For example, if a patient receives a course in May 2020 and a course in May 2021, their follow-up for first course will run from May 2020 to May 2021. Then, their index date will change to May 2021 and follow-up for monitoring will continue anchored on new index date for course 2. Adherence will be stratified by course number so that an understanding of continued monitoring can be gained.

For patients initiated on treatment prior to 2020, such as continuing users, follow-up for adherence to monitoring will begin from SmPC change (January 2020) onwards, anchored on the original index date.

		Monthly				Every three months	
	N	FBC	Serum Creatinine	Serum transaminases	Thyroid function	Urinalysis with microscopy	Thyroid function
UK	Х	X%	X%	X%	X%	n/a	X%
Germany	Х	X%	X%	X%	X%	X%	X%

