Belgium	Х	X%	X%	X%	X%	X%	X%
Czech Republic	Х	X%	X%	X%	X%	X%	X%
Pooled*	Х	X%	X%	X%	X%	X%	X%

Table 9: Percentage adherence to long-term monitoring after infusion in each data source

*Pooling of results across data sources only if heterogeneity allows

FBC= Full Blood Count; UK=United Kingdom

As described above, adherence will be calculated at the patient level, across all courses. Percentage adherence will be calculated on the continuous scale and the full distribution of adherence will be presented as the main results, as highlighted in Table 7 to Table 9.

To gain further understanding of monitoring patterns the following analyses will be run:

- Adherence will be stratified by new and continuing use;
- Adherence will be stratified by course number;
- Categorical thresholds will be defined for adherence (all objectives). For example, if a patient receives ≥80% of recommended monitoring they could be classified as adherent. The percentage of patients meeting other arbitrary thresholds for adherence e.g., thresholds ranging from ≥60% to ≥95% will be calculated. These thresholds will be further defined in the statistical analysis plan.

The main analysis will measure adherence to monitoring using a 15-day tolerance window for monthly testing and a 30-day tolerance window for testing that occurs every three months. These windows were chosen to reflect the real-world provision of care and to accommodate the deviations in monitoring that occur as part of routine practice. The feasibility analysis included sensitivity analyses using a 7-day window for the monthly testing and a 15-day window for the testing that occurs every three months (as described in Protocol V1.6, June 2022). These analyses were found to not be appropriate and were therefore removed from the protocol.

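### Objective 2b adherence is written as tests divided by testing periods, so repeat tests can offset untested periods and the result can exceed 100%; Table 2 describes a per-period measure instead

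*Protocol*

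**What the plan says.** Section 9.8.2 defines patient-level adherence for the four monthly tests with "the number of each specific test carried out within designated testing periods" as numerator and that patient's total number of testing periods as denominator. The thyroid bullet has the same form: tests within testing periods, "divided by the total number of tri-monthly testing periods for each patient".

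The abstract restates the measure for objective 2b as "numerator=number of specific tests received, denominator=number of testing periods required". Here the condition that a test must lie inside a testing period is absent.

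Table 2 in section 9.3, to which that section refers for the outcome definitions, words monthly monitoring as "Evidence that each test is carried out within the designated testing period", with parallel wording for thyroid function. That reads as yes or no for each period.

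The windows are a "15-day tolerance window for monthly testing and a 30-day tolerance window for testing that occurs every three months". The patient percentages are then averaged ("Adherence to safety monitoring will be calculated for each test and for each patient and then the average for each test across all patients") and also cut at thresholds, for example "if a patient receives ≥80% of recommended monitoring they could be classified as adherent", with other cut-offs from 60% to 95%. Nothing in these places caps the ratio or says how a second test in the same period is handled.

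**The concern.** Objective 2b asks whether monitoring took place every month, or every three months for thyroid function. The safety-relevant quantity is therefore the period without a test. A ratio of tests to periods measures testing volume: two blood counts in one month and none in the next look the same as one in each.

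The percentage feeds the Table 9 averages and the adherence categories, so a patient with real gaps can be classed as adherent, and in the averages one patient's surplus tests can offset another patient's missed periods.

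The wording also matters operationally. Under sections 9.7 and 9.7.2 the local operating protocols derive from this protocol, the scripts follow from them, and only aggregate tables leave each data source. A numerator programmed literally at one source could not be corrected centrally.

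**Working it through.** The protocol states no numerical result for objective 2b, so there is no figure to reproduce. The check applies the written ratio to assumed test dates and compares it with the share of periods covered.

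**Inputs from section 9.8.2.** Monthly windows: index + 30k ± 15 days. Thyroid windows: index + 90k ± 30 days.

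**Formulas.**
- As written: tests falling in any window ÷ number of windows.
- Per period (Table 2 reading): windows holding at least one test ÷ number of windows.

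**Results for single patients (test patterns assumed).**

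| Pattern | As written | Per period |
|---|---|---|
| A. Monthly, 12 periods: two tests in each of months 1–6, none in 7–12 | 12/12 = 100% | 6/12 = 50% |
| B. Monthly, 12 periods: one test in every month plus 3 repeats | 15/12 = 125% | 12/12 = 100% |
| C. Monthly, 12 periods: months 1–8 tested plus 2 repeats | 10/12 = 83.3% | 8/12 = 66.7% |
| D. Thyroid, 4 periods: two tests in each of periods 1–2, none in 3–4 | 4/4 = 100% | 2/4 = 50% |

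Pattern C passes a threshold of 80% as written and fails it per period.

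**Effect on the average.** Take patient B (125%) and a patient with single tests in 9 of 12 months (9/12 = 75%). As written, the mean is (125 + 75)/2 = 100%. Per period it is (100 + 75)/2 = 87.5%.

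**Direction.** Each covered window needs at least one test. So for a given set of in-window tests the written ratio is at or above the share of periods covered, provided no test lies in two windows.

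**Boundary days.** 30 ± 15 is days 15–45 and 60 ± 15 is days 45–75, so they share day 45; later monthly windows share days 75, 105, 135 and so on. As a test count, a day-45 test counts once. As a period count, it would cover two periods unless a rule assigns it to one. The thyroid windows, days 60–120 and 150–210, do not touch.

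**Abstract against 9.8.2.** A thyroid test on day 130 lies between those two windows. It counts as a test received under the abstract and does not count under 9.8.2.

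**The case against.** The strongest reply is that the documents already show the intended measure. Section 9.3 points to Table 2 for the outcome definitions, Table 2 reads per period, section 9.8.2 introduces its ratio as an example, and a second test in the same month is hardly recommended monitoring. Repeat handling could sit in the analysis plan or local scripts. Objective 2b is also secondary in a descriptive study, and the full distribution of adherence is to be shown, so values above 100% would be seen.

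Much of this stands as evidence of intent, but it does not remove the conflict. The count ratio is stated in both 9.8.2 and the abstract, and on this measure 9.8.2 defers only the thresholds to the analysis plan. A distribution exposes values above 100%, but not a patient such as C, whose 83% looks ordinary. The sensitivity analysis counted from the last test date (section 9.8.4) moves the windows and says nothing on repeats.

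A reader might infer more than the documents support:
- **A large bias.** Treating test dates as random would give a wide gap between the two measures, but nothing supports that assumption. Monitoring is scheduled, TREAT-MS patients carry reminder cards, and section 9.9 reports that test dates around the intended day supported the windows.
- **Repeats clustering after abnormal results.** No section says so.
- **Reported adherence too high overall.** Sections 9.5.1 and 9.11 describe an opposite influence: Czech primary-care tests are not systematically captured.
- **The day-45 overlap as a fault of the written ratio.** It arises only once periods are counted, and only for monthly windows.

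**Conclusion.** The point holds as a defect in the stated definition. Section 9.8.2 and the abstract give a ratio that repeat tests can inflate and that has no upper limit; Table 2 describes a different, per-period measure; and the abstract also drops the in-window condition.

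The examples show what the formula permits: 83% instead of 67%, 100% instead of 50%, or 125%. They are not estimates of what the data sources will show. With no repeat-test rate in the documents, the size of the bias is unknown. Its direction is known only for a given set of in-window tests and apart from shared boundary days. If the local scripts already count periods, the text is wrong but the results are not.

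**What to change.** - **Definition.** In 9.8.2 (monthly and thyroid) and the abstract, set the numerator to the number of testing periods with at least one qualifying test, at most one per period, and the denominator to the number of testing periods within follow-up. This agrees with Table 2. Use it for the averages and the threshold categories.
- **Boundary days.** Assign days 45, 75 and so on to one monthly period only, for example with windows of days 15–44 and 45–74. The thyroid windows need no such rule.
- **Czech, UK and German sources.** Check the scripts against this definition and amend them where they count tests.
- **Belgium.** No new analyses will be run there (sections 9.2 and 9.5.2), so the scripts cannot be changed. State which definition the 2022 results used. If it was a test count, flag it in Table 9 and do not pool it with the others. In Table 5 Belgium holds 529 of 1976 objective 2b patients, 529/1976 = 27%.

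The cost is a few sentences in the protocol and a small edit to up to three sets of scripts. The downside is that reported adherence may be lower and the Belgian figures may not be comparable with the rest.
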